3. INTRODUCTION

As per ICH E9, the purpose of this document is to provide a more technical and detailed elaboration of the principal features of the analysis described in the protocol, and to include detailed procedures for executing the statistical analysis of the primary and secondary variables and other data.

This TSAP assumes familiarity with the Clinical Trial Protocol (CTP), including Protocol Amendments. In particular, the TSAP is based on the planned analysis specification as written in CTP Section 7 “Statistical Methods and Determination of Sample Size”. Therefore, TSAP readers may consult the CTP for more background information on the study, e.g., on study objectives, study design and population, treatments, definition of measurements and variables, planning of sample size, randomization.

SAS® Version 9.2 (or later version) will be used for all analyses.

4. CHANGES IN THE PLANNED ANALYSIS OF THE STUDY

The changes to the planned analysis are as follows:

The CTP lists primary endpoint AUC0-tz as AUC0-336, which is a typographical error and has been corrected as AUC0-504 in its second revision.

The CTP specifies that “in case that MTD of co-administration of itraconazole and volasertib is less than 300mg, dose will be considered in the ANOVA model to correct for the different starting doses of the patients.” However, after first three patients treated on the initial dose level 300mg for the combination therapy, MTD de-escalated immediately to 250mg and all subsequently enrolled patients were treated on 250mg in cycle 1. Very few patients had further intra-individual dose reduction to 200mg during cycle 2 mono-therapy. Due to the sparse data available on the dose levels other than the MTD 250mg, the primary analysis set for pharmacokinetic endpoints will be restricted among the patients who were treated on 250mg in both cycle 1 and cycle 2. The single patient who was treated on 300mg in both cycle 1 and cycle 2 will also be included in the primary analysis. In addition, a sensitivity analysis will be conducted by including patients with intra-dose reduction during cycle 2 after dose normalization.

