5.5.1 Pharmacokinetic endpoint(s)

Pharmacokinetic parameters will be evaluated by means of noncompartmental analysis. The derivation of pharmacokinetic parameters is described in detail in the internal SOP 001-MCS-36-472_RD-01.

Primary endpoints (volasertib and CD 10899):

[figure not shown]
- maximum measured plasma concentration (C_{max})
- area under the plasma concentration-time curve over the time interval from zero to the last quantifiable drug plasma concentration after dose administration (AUC_{0-tz})

Secondary endpoint (volasertib and CD 10899):

- area under the plasma concentration-time curve over the time interval from zero extrapolated to infinity ($AUC_{0-\infty}$)

Proprietary confidential information.

© 2017 Boehringer Ingelheim International GmbH or one or more of its affiliated companies. All rights reserved.
This document may not - in full or in part - be passed on, reproduced, published or otherwise used without prior written permission.

All pharmacokinetic measurements will be performed only in first two treatment cycles.

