7. STATISTICAL METHODS AND DETERMINATION OF SAMPLE SIZE

7.1 STATISTICAL DESIGN - MODEL

Objectives

The primary objective of the present study is to investigate the influence of co-administration of itraconazole, a potent dual inhibitor of cytochrome P450 3A4 and P-gp, and volasertib (Test, T) on the pharmacokinetic profile of volasertib without co-administration of itraconazole (Reference, R). Therefore the relative bioavailability of volasertib will be assessed.

Design

The study will be conducted according to an open-label, randomised, fixed sequence design. The comparisons will be intra-individual (each subject serves as his own control) and the precision is therefore expected to be higher than with a between-subject comparison [[R94-1529](#)]. The uncontrolled design with respect to potential time effects is unavoidable but still expected to deliver valid results on the volasertib PK.

Primary endpoints

Relative bioavailability of volasertib and its main metabolite CD 10899 is primarily to be determined on the basis of the parameters AUC_{0-tz} , and C_{max} (see [Section 5.5.1](#)). The derivation of these primary parameters is given in the internal SOP 029-DCP-102.

Secondary endpoints

The $AUC_{0-\infty}$ of volasertib and its main metabolite CD 10899 will be statistically assessed using the same methods as described for the primary endpoints.

The derivation of these PK parameters is presented in the internal SOP 029-DCP-102.

Safety and tolerability will be determined on the basis of the following parameters: adverse events, ECG, and clinical lab tests.

Proprietary confidential information.

© 2017 Boehringer Ingelheim International GmbH or one or more of its affiliated companies. All rights reserved.
This document may not - in full or in part - be passed on, reproduced, published or otherwise used without prior written permission.

The derivation of these PK parameters is presented in the internal SOP 001-MCS-36-472_RD-01.

If deemed necessary, statistical assessments will be conducted.

Model

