Description of change		Change 1: 175 mL vial was added with content. Change 2: Content for 100 mL vial was deleted for daily dose.
Rationale for change		Changes 1: In next IMP re-supply 175 mL vials will be provided instead of 100 mL; both vial sizes will be permitted to usage. Change 2: Content was applicable only for 100 mL vial.
Section to be changed		Table 4.1.4.1: 1 Treatments to be administered in the first treatment cycle
Description of change		175 mL vial was added with content as well as no. of vial to be used.

Proprietary confidential information.

© 2017 Boehringer Ingelheim International GmbH or one or more of its affiliated companies. All rights reserved.
This document may not - in full or in part - be passed on, reproduced, published or otherwise used without prior written permission.

Rationale for change	As of next IMP re-supply both vial sizes will be permitted to usage.
Section to be changed	Table 4.1.4.2: 1 Treatments to be administered in the second treatment cycle
Description of change	175 mL vial was added with content as well as no. of vial to be used.
Rationale for change	As of next IMP re-supply both vial sizes will be permitted to usage.
Section to be changed	4.1.6 Packaging, labelling, and re-supply
Description of change	Change 1: 175 mL was also added as well as 350 mg respectively.
Rationale for change	In next IMP re-supply 175 mL vials will be provided instead of 100 mL.
Section to be changed	5.2.1 Endpoint(s) of safety
Description of change	Adverse event was deleted as endpoint, however added that it will be also assessed.
Rationale for change	Adverse event is not an endpoint.
Section to be changed	5.2.2.1 Definitions of adverse events
Description of change	Isolated elevation of AST and / or ALT clarified.
Rationale for change	Typo correction.
Section to be changed	5.5.1 Pharmacokinetic endpoint(s)
Description of change	Change 1: SOP number corrected. Change 2: 'Objective' was changed to 'endpoint'. Change 3: AUC _{0-tz} 336 hours changed to the last quantifiable drug plasma concentration after dose administration. Change 4: Under Other objectives the last three parameters were deleted. Change 5: A sentence was added for PK measurements.

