2. LIST OF ABBREVIATIONS

Include a list of all abbreviations used in the TSAP

Term	Definition / description
AE	Adverse Event
AUC	Area under the plasma concentration-time curve
AUC _{0-∞}	Area under the plasma concentration-time curve over the time interval from 0 to infinity
AUC _{0-tz}	Area under the plasma concentration-time curve over the time interval from 0 to the time of the last quantifiable data point
BLQ	below the limit of quantification
bpm	Beats per minute
CI	Confidence Interval
CL	Total clearance of the analyte in plasma following intravenous infusion
C _{max}	Maximum measured concentration of the analyte in plasma
C _{max,ss}	Maximum measured concentration of the analyte in plasma at steady state
C _{pre,ss,N}	Predose steady state plasma concentration of the analyte in plasma immediately before administration of the Nth dose
CML	Local Clinical Monitor
CRA	Clinical Research Associate
CRF	Case Report Form
CTCAE	Common Terminology Criteria for Adverse Events
CTMF	Clinical Trial Master File
CTP	Clinical Trial Protocol
CTR	Clinical Trial Report
CYP3A4	Cytochrome P ₄₅₀ 3A4
DDI	Drug-drug interaction
DILI	Drug-induced Liver Injury
DMC	Data Monitoring Committee
DRT	Dose Reducing Toxicity
ECG	Electrocardiogram
ECOG	Eastern Cooperative Oncology Group
eCRF	Electronic Case Report Form

Term	Definition / description
EDC	Electronic Data Capture
EDTA	Ethylenediaminetetraacetic acid
EudraCT	European Clinical Trials Database
FAS	Full Analysis Set
GCP	Good Clinical Practice
HR	Heart rate
IB	Investigator's Brochure
IEC	Independent Ethics Committee
IMP	Investigational Medicinal Product
IRB	Institutional Review Board
ISF	Investigator Site File
i.v.	Intravenous
IVRS	Interactive Voice Response System
IWRS	Interactive Web-based Response System
MDR1	Multidrug resistance protein 1
MedDRA	Medical Dictionary for Drug Regulatory Activities
MRT	Mean residence time after intravenous infusion
ms	Milliseconds
MST	Medical Subteam
MTD	Maximum Tolerated Dose
NOA	not analyzed
NOP	no peak detectable
NOR	no valid result
NOS	no sample
OPU	Operative Unit
PD	Progression of Disease
PG	Pharmacogenomics
PLK	Polo-like kinase
p.o.	per os (oral)
PCC	Protocol Challenge Committee

Term	Definition / description
P-gp	P-glycoprotein
PR interval	ECG interval from the start of P wave to the start of the QRS complex
q.d.	quaque die (once a day)
QRS complex	Combination of a Q wave, an R wave, and an S wave
QT interval	ECG interval from the start of the QRS complex to the end of the T wave

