5. ENDPOINTS

5.1 PRIMARY ENDPOINTS

Relative bioavailability of volasertib and its main metabolite CD10899 will be investigated primarily on the basis of the following pharmacokinetic parameters:

CTP: *The following primary endpoints will be determined for volasertib and its main metabolite CD 10899:*

- AUC_{0-tz} *(area under the plasma concentration-time curve of the analyte in plasma over the time interval from zero to 504 hours or last actual measure time)*
- C_{max} *(maximum measured plasma concentration of the analyte in plasma)*

The primary objective is to estimate the relative bioavailability of a single dose of volasertib and its main metabolite CD10899 when administered alone (volasertib monotherapy) compared with co-administered with itraconazole (200mg once daily) in cancer patients with various solid tumors. The relative bioavailability is primarily to be determined on the basis of geometric mean ratios of the primary pharmacokinetic endpoints AUC_{0-tz} and C_{max} measured under the combination therapy period relative to mono therapy period. The derivation of these primary pharmacokinetic endpoints is given in the internal SOP 001-MCS-36-472_RD-01([6](#)).

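### Does the SAP's statement that the protocol redefined the primary AUC as AUC0-504, together with two different SOP numbers, leave the primary endpoint unclear?

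*SAP*

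**What the plan says.** Four places describe the upper limit of the primary AUC.

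- Protocol 5.5.1 (current text): AUC0-tz runs "over the time interval from zero to the last quantifiable drug plasma concentration after dose administration".
- Protocol section 11, global amendment 2, entry for 5.5.1: "336 hours changed to the last quantifiable drug plasma concentration after dose administration".
- SAP section 4: the 336-hour definition was a typographical error that "has been corrected as AUC0-504 in its second revision".
- SAP 5.1, under a label attributing the text to the protocol: "from zero to 504 hours or last actual measure time".

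The SAP's abbreviation list gives AUC0-tz as the area "from 0 to the time of the last quantifiable data point". The protocol's list says the same.

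On derivation, Protocol 7.1 states: "The derivation of these primary parameters is given in the internal SOP 029-DCP-102". SAP 5.1 states: "The derivation of these primary pharmacokinetic endpoints is given in the internal SOP 001-MCS-36-472_RD-01". Protocol 5.5.1 names the same SOP as SAP 5.1.

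**The concern.** SAP section 4 is the record of how the analysis departs from the protocol. There it credits the protocol with a fixed-window AUC that the protocol does not contain, and this concerns a primary endpoint for both analytes. A fixed 0 to 504 hour area is a different quantity from AUC0-tz whenever the last sample is early, late, missing or below the limit of quantification. A programmer who took the sentence literally could compute the wrong parameter, and a report author could repeat the wrong description.

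The SOP mismatch seems to add to this, because the document that would settle the derivation is itself cited inconsistently. The SAP says that "the TSAP is based on the planned analysis specification as written in CTP Section 7", and section 7 is where the other SOP number appears.

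**Working it through.** No planned figure is involved, so the check is a comparison of texts in three steps.

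**1. Which definition governs?**

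| Source | Upper limit of the primary AUC |
|---|---|
| Protocol abbreviations | last quantifiable data point |
| Protocol 5.5.1 | last quantifiable concentration |
| Protocol section 11, amendment 2 | 336 h replaced by last quantifiable concentration |
| SAP abbreviations | last quantifiable data point |
| SAP 7.4 (model) | AUC0-tz, no hour limit |
| SAP 5.1 | 504 h or last actual measurement time, under the symbol AUC0-tz |
| SAP 4 | AUC0-504 |

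Only SAP 4 gives a fixed window, and even that sentence calls the endpoint AUC0-tz. Protocol 3.1 explains where the number comes from: PK sampling continues until 504 hours after the start of infusion. SAP 5.1 therefore reads as a loose way of saying up to the last measurement. Protocol 7.1, which the SAP follows, sends the reader to 5.5.1 for these parameters and so to the correct definition.

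**2. Could an analyst compute AUC0-504 by following the SAP?** Not without adding a rule.

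- SAP 6.7 uses actual sampling times. Protocol 5.4.1 allows ±5% of the nominal time. At 504 h that is 0.05 × 504 = 25.2 h, so a compliant last sample may fall anywhere from 478.8 h to 529.2 h.
- A fixed limit of 504 h would then need interpolation or extrapolation, and the SAP specifies neither.
- Protocol 7.4.3 and SAP 6.6.2 ignore values below the limit of quantification after the lag phase. Protocol 7.3.1 uses only concentrations within the validated range. The computed area therefore stops at the last quantifiable concentration, which is AUC0-tz.
- Under the same rules, the last measurement that contributes to the area in SAP 5.1 is also the last quantifiable one.

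If the 504-hour sample is on time and quantifiable, the two definitions coincide. If it is not, the size of the difference depends on the half-life and the quantification limit. The documents give neither.

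**3. Which SOP applies?**

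- 001-MCS-36-472_RD-01 is named in Protocol 5.5.1, SAP 5.1 and SAP 6.6.2, and again later in Protocol 7.1.
- 029-DCP-102 is named only in Protocol 7.1, once for the primary and once for the secondary parameters.
- The amendment 2 log records the SOP number as corrected in both 5.5.1 and 7.1, so as to cite the currently applicable SOP.
- The SAP reference list gives the title of 001-MCS-36-472_RD-01 as noncompartmental analysis, which is the method in Protocol 5.5.1.

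The two mentions of 029-DCP-102 look like leftovers from an incomplete replacement. The SAP itself names the governing SOP for the primary parameters.

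**The case for a change.** The strongest case for acting is that this is a plain error of fact about a primary endpoint, in the section meant to record departures from the protocol, and that a wording edit would cost nothing. SAP 5.1 makes it worse by presenting as protocol text something the protocol does not say. There was also an opportunity to put it right: SAP revision 1 is dated 23 July 2014, after amendment 2 of 12 June 2014, and the error remains in the text.

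The factual part stands. SAP 4 misreports amendment 2, and Protocol 7.1 carries a stale SOP number.

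The step from there to a defect in the plan does not stand. The protocol label in the SAP is not kept for verbatim text elsewhere either. SAP 7.4 adds a repeated-measures description that Protocol 7.1 lacks, and SAP 6.6.2 displays non-quantifiable concentrations as such where Protocol 7.4.2 ignores them. The label alone therefore does not show that a different endpoint was intended. The risk of a misdescribed report depends on an author copying one sentence against Protocol 5.5.1, both abbreviation lists and the endpoint symbol itself. Nothing in the documents shows that the two SOPs differ in content.

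**Conclusion.** This is a clerical slip with no statistical consequence. The primary endpoint is AUC0-tz to the last quantifiable concentration. The protocol says so, the SAP's abbreviation list says so, and the SAP's model uses that parameter. On that reading the effect on the geometric mean ratios and their 90% confidence intervals is zero.

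This rests on two assumptions: that AUC0-tz is programmed as the abbreviation lists define it, and that 001-MCS-36-472_RD-01 is the SOP in force, as the amendment log indicates. A literal AUC0-504 could differ for a patient whose last sample is mistimed or not quantifiable, but the documents do not allow that difference to be sized and the SAP gives no rule for computing it. The endpoint, the model and the planned outputs would all stay as they are, so no change to the plan is called for.

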4.1.3.1 Potential dose reduction

Reduction of starting dose

Initially, patients will be treated sequentially. Single patients will be treated for the first cycle until three patients have completed the first cycle.

Thereafter, cohorts of 3 patients will be treated until the preliminary safety of volasertib in combination with itraconazole is confirmed.

If more than 1 out of 6 patients experiences unacceptable toxicity (DRT, Section 5.2.6) during the first treatment cycle, the dose of volasertib for subsequent patients will be deescalated to 250 mg in the first and second treatment period.

If more than 1 out of 6 patients treated at a volasertib dose of 250 mg experiences unacceptable toxicity during the first treatment cycle, the dose of volasertib for subsequent patients will be further deescalated to 200 mg in the first and second treatment period.

The highest dose for which the incidence of unacceptable toxicity is no more than 1 out of 6 will be used as the dose of volasertib for the first and second treatment cycle of all further patients included in the trial (MTD, cf. [Section 5.2.6](#)).

Dose reduction in individual patients

If a patient experiences unacceptable toxicity (DRT, Section 5.2.6) the patient can continue volasertib treatment at a lower dose if criteria for retreatment are met (see [Section 3.3.5](#)). Each occurrence of DRT will lead to a dose reduction by 50 mg of any subsequent volasertib infusion(s). No dose reduction of volasertib below 200 mg is allowed.

If a patient experiences a DRT at the 200 mg dose, i.e. a dose reduction to <200 mg would be required, the volasertib treatment will be permanently discontinued and the patient will move to the EoT visit.

Proprietary confidential information.

© 2017 Boehringer Ingelheim International GmbH or one or more of its affiliated companies. All rights reserved.
This document may not - in full or in part - be passed on, reproduced, published or otherwise used without prior written permission.

When a dose reduction of volasertib occurs, this applies to all subsequent cycles with no possibility to dose escalation back to the previous dose.

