4.1.3.2 Dose escalation scheme

A patient who is eligible to continue therapy with volasertib beyond the 2nd cycle (see [Section 3.3.5](#)) may either be treated with the original dose or may receive a higher dose in the third and subsequent cycles. The dose can be increased by 50 mg after each cycle ≥ 2 up to a maximum dose of 350 mg in case of clinical benefit and good tolerability in the completed cycle (i.e., non-hematological drug related adverse events of less than CTCAE Grade 2 and / or hematological drug related adverse events of less than CTCAE Grade 3). Dose escalation will occur only upon agreement between investigator and sponsor. Patients should continue on the higher dose in all subsequent treatment cycles if well tolerated. The decision to escalate the dose can be made at the end of cycles ≥ 2 . No dose increases above 350 mg are allowed. After dose escalation to the 350 mg subsequent dose reductions are allowed as per [Section 4.1.3.1](#).

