The statistical model used for the analysis of the primary and secondary PK endpoints will be an ANOVA (analysis of variance) model on the logarithmic scale. This model will include effects accounting for the following sources of variation: 'subject' and 'treatment'. The effect 'subject' will be considered as random, whereas the 'treatment' effect will be considered as fixed. For tests on treatment effects, the denominator sum of squares will be the sum of squares for error in the comparison R – T. The model is described by the following equation

$y_{km} = \mu + s_m + \tau_k + e_{km}$, where

y_{km} = logarithm of response measured on subject m receiving treatment k,

μ = the overall mean,

s_m = the effect associated with the mth subject, $m = 1, 2, \dots, n$,

τ_k = the kth treatment effect, $k = 1, 2, \dots$,

e_{km} = the random error associated with the mth subject who received treatment k.

The subdivision into male / female subjects is not expected to have influence on the intra-individual treatment comparisons and therefore 'sex' is not a model term.

In case the MTD of co-administration of itraconazole and volasertib is less than 300mg, dose will be considered in the ANOVA model to correct for the different starting doses of the patients. The model will take into account the dose proportionality established for volasertib.

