7.2 NULL AND ALTERNATIVE HYPOTHESES

The relative bioavailability of volasertib in combination with itraconazole compared volasertib alone will be investigated descriptively by applying the average bioequivalence method to the ratio between PK parameters (AUC_{0-tz} and C_{max}). No confirmatory hypothesis will be tested.

Proprietary confidential information.

© 2017 Boehringer Ingelheim International GmbH or one or more of its affiliated companies. All rights reserved.
This document may not - in full or in part - be passed on, reproduced, published or otherwise used without prior written permission.

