6.3 PATIENT SETS ANALYSED

- **Treated set (TS):**
This patient set includes all patients who were documented to have taken at least one dose of volasertib. This is the full analysis set population in the sense of ICH-E9. It is used for safety analysis.
- **Primary pharmacokinetic set (pPKS):**
This subject set includes all patients in the TS who were treated on the same dosage

(250mg and 300mg) in the first two cycles and provided complete PK measures without important protocol violations.

- Sensitivity pharmacokinetics set (sPKS)

This subject set includes all patients in the TS who provided complete PK measures in the first two cycles without important protocol violations.

- ECG analysis set (ECGS): This patient set includes all patients in the treated set who provide at least one matching pair of QT measurements available pre-dose and after drug administration. Patients with an artificial pacemaker will be excluded.

Table 6.3: 1 Patient sets analyzed

Class of endpoint	Patient set			
	TS	pPKS	sPKS	ECGS
Primary (PK) endpoints		X	X	
Safety endpoints		X		
ECG endpoints				X
Demographic data/Medical history and Concomitant diagnosis, Concomitant therapy		X		
Important PVs	X			
Disposition		X		

[REDACTED]

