7.4 PRIMARY ENDPOINTS

The relative bioavailability will be investigated based on the PK parameters AUC_{0-tz} and C_{max} for volasertib and its main metabolite CD10899, respectively.

The statistical model used for the analyses will be a repeated measure ANOVA (analysis of variance) model on the logarithmic scale and will be based on both the primary and sensitivity PKS.

CTP: *The statistical model used for the analysis of AUC_{0-tz} , C_{max} of volasertib and CD10899 will be an analysis of variance (ANOVA) model with repeated measure on the logarithmic scale. The effect 'subject' will be considered as random, whereas the effect 'treatment' will be considered as fixed. The model is described by the following equation:*

$y_{km} = \mu + \tau_k + s_m + \varepsilon_{km}$, where

y_{km} = logarithm of response (AUC_{0-tz} or C_{max}) in subject m receiving treatment k ,

μ = the overall mean,

τ_k = the k -th treatment effect, $k = 1, 2$,

s_m = the effect associated with the m -th subject, $m=1, \dots, n$,

ε_{km} = the random error associated with the m -th subject receiving treatment k .

CTP: *The PK parameters AUC_{0-tz} and C_{max} will be log-transformed (natural logarithm) prior to fitting the ANOVA model. The difference between the expected means for $\log(T)$ - $\log(R)$ will be estimated by the difference in the corresponding least square means (point estimate) and 2 sided 90% confidence intervals based on the t -distribution will be computed. These quantities will then be back-transformed to the original scale to give the point estimator*

(geometric mean) and interval estimates for the intra-subject ratio of the geometric means for treatments test and reference.

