As stated in the CTP, in case the tolerable dose of volasertib is less than the initial dose level 300mg, dose would be included as a covariate in the ANOVA model. However, as a consequence of immediate dose de-escalation after first three patients treated on 300mg and two of them discontinued after cycle 1, tolerable dose was de-escalated to 250mg and all subsequently enrolled patients were treated on 250mg. Due to the limited dose levels and sparse data available on 300mg, instead of including dose as an additional covariate in the ANOVA model according to the CTP, primary analysis using ANOVA model on log transformed PK endpoints will be performed based on the clean cohort of patients who were treated on equal dose levels (either 250mg or 300mg) throughout both cycles 1 and 2. In addition, a sensitivity analysis will be performed by including the patients with further intra-individual dose reduction from 250mg to 200mg in cycle 2. In the sensitivity analysis, dose proportionality (BI 1230.5, BI 1230.23) will be applied on individuals with dose reduced to 200mg during cycle 2 volasertib mono therapy to rescale the PK measures. However, since dose proportionality was not established for the combination therapy of volasertib + itraconazole, dose normalization will not be applied on the patient who was treated on 300mg in both cycle 1 and 2.

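### Does leaving out patients whose volasertib dose was cut after cycle 1 bias the headline interaction ratio?

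*SAP*

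**What the plan says.** Protocol 7.1 planned to put dose in the ANOVA if the tolerated dose of the combination fell below 300 mg, to correct for different starting doses: "The model will take into account the dose proportionality established for volasertib". Protocol 7.3.1 would include all evaluable subjects who received volasertib.

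SAP 4 departs from this and says so. After the first three patients the starting dose fell to 250 mg, and very few patients were cut further to 200 mg for cycle 2. Citing sparse data at other doses, the SAP says the "primary analysis set for pharmacokinetic endpoints will be restricted among the patients who were treated on 250mg in both cycle 1 and cycle 2", with the single patient on 300 mg in both cycles added. SAP 6.3 defines the primary set (pPKS) as patients on the same dose "in the first two cycles and provided complete PK measures without important protocol violations". The sensitivity set (sPKS) has the same conditions without the equal-dose rule.

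SAP 7.4 says the ANOVA "will be based on both the primary and sensitivity PKS". For the sensitivity set, "dose proportionality (BI 1230.5, BI 1230.23) will be applied on individuals with dose reduced to 200mg during cycle 2" monotherapy to rescale their PK values. Protocol 7.2 states: "No confirmatory hypothesis will be tested".

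**The concern.** Trace how a patient can come to have a lower dose in cycle 2 than in cycle 1.

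- Protocol 4.1.3.1 lowers an individual's later doses after a dose-reducing toxicity (DRT).
- Protocol 5.2.4 allows or requires a reduction after specified QTcF findings following infusion.
- Protocol 4.1 mentions a reduced dose for unexpected toxicity of the combination.
- Cohort de-escalation in 4.1.3.1 applies to subsequent patients and to both periods, so it creates no within-patient difference.
- Increases cannot explain unequal doses either, since under Protocol 4.1.3.2 a patient "may receive a higher dose in the third and subsequent cycles" at the earliest.

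Every named route to a lower cycle-2 dose is therefore a toxicity in cycle 1, when itraconazole is on board. Membership of the headline set depends on an outcome of the test treatment. If patients with unusually high cycle-1 exposure are the ones who had toxicity, removing them removes large test/reference ratios, and the trial would understate the interaction it exists to measure.

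Sparse data also look like a weak reason. They argue against estimating a dose effect, but multiplying a cycle-2 value by the fixed factor 250/200 estimates nothing, and the SAP accepts that scaling in its sensitivity analysis.

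**Working it through.** The plan has no figure to reproduce: Protocol 7.6 calls 24 evaluable patients conventional, and no margin or power is given. The question is how large the shift could be.

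**Inputs.** From the documents: n = 24, a two-sided 90% interval, and the paired model on the log scale with subject and treatment effects. Assumed, because the documents are silent: k = 1 or 2 patients excluded; between-patient SD sb = 0.3; within-patient SD sw = 0.15 to 0.20; patient-by-treatment SD sd = 0 to 0.15; correlation ρ = 0.5 to 0.8 between a toxicity score and true cycle-1 log exposure; share f of the within-patient variance that is measurement error = 0, 0.5 or 1.

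**Shift.** Suppose the k patients with the highest toxicity score are dropped. A patient's stable level appears in both cycles and cancels in the ratio. Only the part of cycle-1 exposure specific to that cycle matters, with variance v = sd² + (1 − f)·sw². The expected shift in the log ratio is

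ρ · v / √(sb² + v) · z_k,

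where z_k is the mean of the retained standard normal order statistics. For 24 patients the two largest have expectations 1.948 and 1.503, so z_1 = −1.948/23 = −0.0847 and z_2 = −(1.948 + 1.503)/22 = −0.1569.

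Small case with f = 0 (k = 1, ρ = 0.5, sd = 0, sw = 0.15): v = 0.0225, and 0.5 × 0.0225/√0.1125 × (−0.0847) = −0.0028, or −0.28%.

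Large case with f = 0 (k = 2, ρ = 0.8, sd = 0.15, sw = 0.20): v = 0.0225 + 0.0400 = 0.0625, and 0.8 × 0.0625/√0.1525 × (−0.1569) = −0.0201, or −1.99%.

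| Measurement-error share f | 1 excluded | 2 excluded |
|---|---|---|
| 0 | −0.28 to −1.08% | −0.53 to −1.99% |
| 0.5 | −0.15 to −0.79% | −0.28 to −1.46% |
| 1 | 0 to −0.45% | 0 to −0.84% |

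If toxicity follows only the patient's stable exposure, or is unrelated to exposure, the shift is zero.

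**Against the precision.** The interval factor is exp{t(0.95, n − 1)·√((2sw² + sd²)/n)}. At n = 24, t = 1.714, giving 1.077 (sw 0.15, sd 0) to 1.119 (sw 0.20, sd 0.15). At n = 22 it is 1.081 to 1.125. Simulated 90% coverage was 88.1% in the large case above and 89.7% with k = 2, ρ = 0.5, sd = 0, sw = 0.20, f = 0.

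**Wider assumptions.** With 2 to 4 exclusions, within-patient CV 25%, between-patient CV 30%, no patient-by-treatment variance and no measurement error, the shift is about 1 to 3% for ρ = 0.3 to 0.6. The interval factor is then 1.13 to 1.14, and coverage at ρ = 0.6 is 0.88 to 0.89. About 9% appears only at the extreme corner: 4 exclusions, CV 35%, patient-by-treatment CV 20%, ρ = 1.

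**Error from the alternative.** If exposure rises as dose to the power b, scaling k of 24 patients by 250/200 moves the overall log ratio by (k/24)·(b − 1)·ln 1.25 in size. For b = 0.8 or 1.2 that is 0.19% (k = 1) or 0.37% (k = 2), in either direction. The first figure exceeds the smallest non-zero table entries for one exclusion.

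**The case for a change.** The best case for a change is that, in a descriptive trial, the headline estimate is the product. Selecting on a test-cycle event is poor practice even when the effect is small. Protocol 4.1.3 reports no sign of departure from dose proportionality between 200 and 450 mg, which covers both doses. Only monotherapy values would be rescaled, so the SAP's point that proportionality is not established for the combination does not apply. Both analyses are already planned, so exchanging their labels costs almost nothing.

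The selection stands as a matter of fact, and so does the point that sparse data alone do not force the exclusion. Three things weaken the rest.

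- Protocol 7.1 is limited support for scaling, because its dose term addresses different starting doses between patients and not a change within a patient.
- SAP 7.4 gives a second reason: a clean equal-dose comparison, which needs no scaling assumption.
- The dose-proportionality statements concern volasertib. AUC and Cmax of CD 10899 are also primary endpoints, so a swap for volasertib alone would give parent and metabolite different primary sets or leave the metabolite without a single primary result. The direction of any bias for CD 10899 is unknown.

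The exchange would also not recover patients who stopped after cycle 1, such as two of the first three at 300 mg. They are in neither set.

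**Conclusion.** No change is needed. The primary set is selected on a cycle-1 toxicity event, but the consequence is conditional and small: 0 to about 2% on the volasertib ratio with one or two exclusions, and about 1 to 3% under the wider assumptions with ρ = 0.3 to 0.6. Both are well inside the 90% interval. These sizes rest on assumed variances, correlations and counts. They also need toxicity to follow cycle-1 exposure beyond the patient's stable level. The documents tie only QTcF prolongation to Cmax (Protocol 1.2) and show no such link for the haematological DRTs.

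The SAP discloses the restriction, explains it, and fits the same model to the set that restores the cut patients. A reader who compares the two ratios sees directly whether the exclusion mattered, and the planned individual listings and adverse-event tables hold most of the information on who was cut and why. With no margin and no test, the order of the two analyses decides nothing formally. Whether the equal-dose set or the dose-normalised set comes first is a choice on which reasonable statisticians differ.
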